1 CLINICAL PROTOCOL SYNOPSIS

Title	A Phase 2, Multi-Center, Open-Label, Ascending Dose Study on the Efficacy, Safety and Tolerability of Perhexiline in Patients with Hypertrophic Cardiomyopathy and Moderate-to Severe Heart Failure with Preserved Left Ventricular Function
Protocol Number	HML-PHX-005
Phase	2
Sponsor	Heart Metabolics Ltd.
Investigational Product	Perhexiline
Indication	Treatment of moderate-to-severe symptomatic hypertrophic cardiomyopathy (HCM)
Study Centers	Approximately 10 US sites
Objectives	
Primary:
 
 To evaluate the effect of perhexiline (PEX) on the change from baseline of a functional status measure (VO₂MAX) in patients with HCM and moderate-to-severe heart failure with preserved left ventricular (LV) function following repeat dosing with PEX for 112 days 
Secondary:
 
 To evaluate the ascending dose-response effect on the change from baseline of VO₂MAX in patients with HCM and moderate-to-severe heart failure with preserved LV function following repeat dosing with PEX for 112 days To evaluate the electrocardiographic (ECG) response, tolerability and safety of orally administered PEX in patients with HCM and moderate-to-severe heart failure with preserved LV function following repeat dosing with PEX for 112 days
Endpoints	
Primary:
 
 Change from baseline of VO₂MAX at the end of Period 2 
Secondary Endpoints:
 
 The change from baseline of VO₂MAX at the end of study-drug dosing Period 1 compared to the change from baseline at the end of Period 2. An evaluation of the change in VO₂MAX at the end of study-drug dosing Period 1 compared to baseline will be performed The change from baseline of the QTcF interval at the end of study-drug dosing Period 1 compared to the change from baseline at the end of Period 2 The change from baseline at the end of study-drug dosing Period 2 in the Six-Minute Walk Test (6MWT) and change from baseline at the end of study-drug dosing Period 1 compared to the change from baseline at the end of Period 2 Safety data (adverse events [AE], routine laboratory safety test of blood, ECG abnormalities, vital signs, and concomitant medication and patient withdrawals) during study-drug dosing Period 1 compared to Period 2

	
Exploratory endpoints:
 
 • Change from baseline of other ECG variables at the end of study-drug dosing Period 1 compared to the change from baseline at the end of study-drug dosing Period 2 • Change from baseline of HbA1c at the end of study-drug dosing Period 1 compared to the change from baseline at the end of study-drug dosing Period 2

Study Design
	
This is a Phase 2, open label study that will enroll approximately 33 patients with HCM who are unable to exercise more than 75% of their maximum predicted capacity during Cardio-Pulmonary Exercise Testing (CPEX) at Screening (Figure 1.1). They will then be started on 70 mg PEX daily and dose titrated to a plasma level of 100-300 ng/ml over 8 weeks (Period 1). CPEX will be repeated, and then the dose will be titrated up to a plasma level of 300-500 ng/ml PEX for a further 8 weeks (Period 2). CPEX will be assessed at the end of Period 2. The patients will then complete a 4-week safety observation period before study termination. Approximately 30 patients are projected to complete the study.
 
Figure 1.1 Study design for Periods 1 and 2
 
33 HCM Patients with $VO_{2\text{MAX}} < 75\%$ Predicted during CPEX
 
Starting Dose 70 mg qd
 
Period 1 8 Weeks
 
Period 2 8 Weeks
 
Follow Up 4 Weeks
 
Dose adjust to Plasma level 100 – 300 ng/mL
 
Dose adjust to Plasma level 300 – 500 ng/mL
 
Off Drug
 
CPEX CPEX CPEX

Number of Patients
	
Approximately 33; anticipate 30 to complete full 16 weeks of dosing

Target Population
	
Patients with HCM and moderate to severe heart failure with preserved LV function

Length of Study
	
Approximately 24 weeks as follows:
 
 • Screening: 4 weeks • Period 1: 8 weeks • Period 2: 8 weeks • Follow-up: 4 weeks

Investigational Drug
	
PEX is available as 35 mg tablets


Study Drug Dosing
	
All patients will receive 70 mg daily during weeks one and two in Period 1. Formal dose adjustments will not be done during this time, although the PEX dose may be decreased at any time for suspected elevated PEX levels or related AE. Patients should take study drug in the evening, preferably between 8 and 11p.m (with the exception of the first dose of study drug, which will be administered under the supervision of the study-site staff).
 
On the morning of day 8 (± 1 Day), a blood sample to determine the levels of PEX and cis- and trans-hydroxy-perhexiline (CIS, TRANS) will be obtained. Results for PEX and CIS will be reported to the study sites in order to:
 
 • Withdraw phenotypic poor metabolizers (PMs) from the study 
On the morning of day 15 (± 1 Day), a blood sample to determine the levels of PEX, CIS, and TRANS will be obtained. Results for PEX and CIS will be reported to the study sites to:

- Evaluate the CIS:PEX ratio. Patients with a ratio <0.4 will be further evaluated and the patient status will be discussed with the Medical Monitor.
- Determine dose adjustment starting after completion of a minimum of 13 days of study-drug dosing.

PEX, CIS, and TRANS Levels will continue to be measured every other week (Weeks 4, 6, 8, 10, 12 and 14) in order to guide dose adjustment according to Table 1.1 (below) and to evaluate the CIS:PEX ratio. At the conclusion of Period 2 (end of Week 16), an additional blood sample will be obtained to determine the levels of PEX, CIS, and TRANS.

A final blood sample will be obtained at the conclusion of the 4-week safety follow-up period (end of week 20) and plasma levels of PEX, CIS and TRANS determined.

Dose Adjustment Guidelines and Algorithm

1. All patients will receive 70mg/day for the first 14 days. Formal dose-adjustments will start at the end of Week 2 / Start of Week 3 in Period 1. However, the dose may be decreased at any time for suspected elevated PEX levels or related AE.
2. Available dose levels will include:
 - a. Period 1: 35, 70, 105, 140, 175, and 210 mg (tablet strength is 35 mg)
 - b. Period 2: 35, 70, 105, 140, 175, 210, 245, & 280 mg (tablet strength is 35 mg)
3. In general, only one dose adjustment should be made per two-week period. If the PI thinks an additional dose adjustment should be made, the PI should contact the Medical Monitor.
4. Upon notification of a dose adjustment the site should contact the patient as soon as possible to initiate dose adjustment according to Table 1.1, below.
5. To achieve the higher target range for PEX in Period 2, the dose will initially be adjusted based on the plasma PEX level measured at Week 6 in Period 1. This dose adjustment will be performed at the Week 8 visit (start of Period 2) in accordance with the Period 2 column in Table 1.1, below. **Important:** Any change made at Week 6 will need to be accounted for when adjusting the dose at Week 8.

Table 1.1 Dose-adjustments from Week 2, Period 1 and throughout Period 2

Systemic Perhexiline Level (PEX) (ng/mL)**	Period 1 (Weeks 2 – 8) Target Range 100-300 ng/mL Start Dose of 70 mg/day, 2 tablets per day (Tablets to be taken orally in the evening) Maximum Dose 210 mg (6 tablets)	Period 2 (Weeks 9 – 16) Target Range 300-500 ng/mL Start dose will be the dose-adjustment decision based on the Period 1, Week 6 level of PEX† (Tablets to be taken orally in the evening) Maximum Dose 280 mg (8 tablets)
< 50	+2 tablets per day#	+2 tablets per day#
50 to 100	+1 tablet per day#	+2 tablets per day#
101 to 200	No change	+1 tablet per day#
201 – 300	No change	+1 tablet per day#
301 – 400	-1 tablet per day*	No change
401 – 500	-2 tablets per day*	No change
501 – 600	-3 tablets per day*	-1 tablet per day*
601 – 700	Discontinue for 1 day, and -3 tablets per day*	Discontinue for 1 day, and -2 tablets per day*

	701 - 900	Discontinue for 3 days , and -4 tablets per day*	Discontinue for 1 day , and -3 tablets per day*
	901 - 1200	Discontinue for 7 days , and -5 tablets per day*	Discontinue for 3 days , and -4 tablets per day*
	> 1200	Discontinue for 7 days , and -5 tablets per day*	Discontinue for 7 days , and -5 tablets per day*
	
# Unless the patient has already reached the highest daily dose of six (6) tablets or 210 mg in Period 1 and eight (8) tablets or 280 mg in Period 2
 
* The lowest daily dose is one (1) tablet per day or 35 mg.
 
** Blood sampling for plasma PEX, CIS and TRANS measurement should be obtained approximately 12 hours following dosing on the previous day. Results for systemic PEX and CIS levels will be reported to the study sites.
 
† Any change made at Week 6 will need to be accounted for when adjusting the dose at Week 8.
 
6. Dose adjustment for QTcF/JTcF prolongation (regardless of PEX levels reported, unless the PEX levels and dose adjustment algorithm result in a dose reduction or discontinuation of a greater magnitude) will proceed as follows for EITHER:
 
a. Patients with a QRS interval \leq 100 msec WITH;
 
 • A prolonged QTcF > 540 msec OR, • An increase in QTcF > 75 msec over baseline AND QTcF > 500 msec 
b. Patients with a baseline OR any on-study QRS interval > 100 msec WITH:
 
 • An increase in the JTcF > 75 msec over baseline AND the JTcF > 410 msec OR • An on-study JTcF interval > 450 msec 
The dose of study drug will be stopped for 2 days and the daily dose subsequently reduced by 35 mg (for patients receiving \leq 105 mg) or 70 mg (for patients receiving \geq 140 mg) and restarted only if the QTcF/JTcF measurement has fallen back into the acceptable range for continued dosing. If the QTcF/JTcF measurement has NOT fallen back into the acceptable range after stopping drug for 2 days, the process of holding study drug and rechecking the ECG every 2 to 3 days will continue until the QTcF or JTcF limits are not exceeded and at which time study drug may be restarted at the reduced dose. The dose of study drug will not be increased any further during either Period 1 or Period 2 if a dose reduction for QTcF or JTcF prolongation is required.
		
Safety Assessment	
A Study Monitoring Team will be established to review all available data in listings approximately every 2 months (until the study is completed) following 25% enrollment in the study with an emphasis on observed outcomes related to patient safety and tolerance (i.e., AEs, adverse device effects (ADE), vital signs measurements, ECGs, laboratory assessments, and concomitant medications). These listings will be reviewed by the Study Monitoring Team to determine whether the dosing regimen should be altered during the course of the study or whether any other protocol modifications should be instituted to ensure the safety of the patients. The Study Monitoring Team will include at a minimum an independent cardiologist, the Medical Monitor (Contract Research Organization [CRO]), the study biostatistician (CRO), and a Sponsor representative.
		

Inclusion Criteria	
1. General Criteria
 
 a. Adult, at least 18 years of age b. Able and willing to give written informed consent 
2. Cardiomyopathy-related Criteria
 
 a. Hypertrophic cardiomyopathy with moderate-to-severe heart failure meeting all of the 2011 American College of Cardiology Foundation/American Heart Association Criteria for the Diagnosis of Hypertrophic Cardiomyopathy [Gersh et al., 2011]. b. Left ventricular hypertrophy (LVH) with maximum LV wall thickness \geq 15 mm measured within the past 12 months without an alternative explanation. c. Left ventricular ejection fraction \geq 50% d. Able to perform exercise testing but unable to exceed 75% of the predicted age-adjusted maximum level (as determined by VO₂MAX measured during Screening CPEX). VO₂MAX will be determined again at Baseline and must not exceed \pm20% of the Screening VO₂MAX. e. Normal sinus rhythm at Screening and Baseline (atrial fibrillation pattern acceptable for patients with chronic atrial fibrillation and controlled ventricular response) f. If taking any medications for the treatment of HCM (including beta-blockers, calcium channel blockers, diuretics), the medication has been taken at a stable dose for at least 60 days prior to screening and will be continued at the same dose throughout the study
Exclusion Criteria	
1. General Exclusion Criteria:
 
 a. Pregnant women, women who intend to become pregnant, or woman who are not practicing contraception, either pharmacologically or with a barrier method b. Lactating women c. CYP2D6 Poor Metabolizer (PM) status, based on genotype known prior to Screening, or as determined by genotype assessed at Screening. CYP2D6 Poor Metabolizer status will be reported by the central laboratory in the screening report according to the Clinical Pharmacogenetics Implementation Consortium (CPIC) guidelines [Crews et al., 2014]. d. Any patient who regularly takes a medication known to be a strong inhibitor of CYP2D6 (bupropion, fluoxetine, paroxetine, quinidine, or ritonavir) e. Any concomitant disease, condition, or treatment that could interfere with the conduct of the study, or that would, in the opinion of the investigator or sponsor, pose an unacceptable risk to patients and/or interfere with the interpretation of study data. f. History of a known toxic or inflammatory peripheral neuropathy, such as mononeuritis multiplex, acute or chronic inflammatory demyelinating polyneuropathy, axonal sensorimotor neuropathies, drug-related neuropathy or neuritis, or diabetic neuropathy (history of a compression neuropathy, such as carpal tunnel syndrome, is acceptable) g. Poorly controlled diabetes mellitus (e.g., HbA1c > 9.0%) h. Clinically severe chronic obstructive pulmonary disease (i.e., Chronic Obstructive Pulmonary Disease requiring home oxygen or history of intravenous or oral steroid use)

	
 i. History of a known chronic liver disease including cirrhosis of any cause, or chronic hepatitis B or hepatitis C j. History of porphyria k. History of recurrent hypoglycemia l. Active infection requiring antibiotics m. Life expectancy of less than 2 years n. Evidence of an active or suspected cancer or systemic treatment within the previous 5 years for a malignancy, except for skin squamous cell or basal cell carcinomas that did not require systemic therapy and are considered to be cured o. History of substance abuse, including alcohol or illicit drugs within the past 12 months 
2. QT Interval-Related Exclusion Criteria:
 
 a. Personal history of congenital long QT syndrome, Torsade de Pointes (TdP), or drug-induced long QT b. On the basis of the mean of triplicate ECGs at screening or baseline: 
 i. QTcF > 500 msec if QRS ≤ 100 msec ii. JTcF > 410 msec if QRS > 100 msec c. Serum potassium < 3.8 mEq/L (may be repeated up to two times during screening after attempts at medical management) d. Currently taking a medication with known risk of QT prolongation and TdP as listed in the “Known Risk of TdP” Risk Category on www.crediblemeds.org [Woosley and Romero]. e. If possessing a pacemaker or Implantable Cardioverter Defibrillator (ICD), ventricular pacing > 10% of the time 
3. Other Exclusion Criteria:
 
 a. Abnormal safety studies of clinical significance at Screening such as: 
 i. Alanine aminotransferase (ALT), aspartate aminotransferase (AST), alkaline phosphatase (ALP), or lactate dehydrogenase (LDH) > 1.5 x upper limit of normal ii. Total Bilirubin > 2.0 x upper limit of normal (unless subject is known to have Gilbert’s syndrome) b. Known hypersensitivity to perhexiline c. Unable or unwilling to comply with the protocol d. Enrolled in another therapeutic trial for HCM 
4. Cardiomyopathy-Related Exclusion Criteria
 
 a. Asymptomatic patients or patients whose symptoms are controlled with medications b. Resting Left Ventricular Outflow Tract (LVOT) gradient > 50 mmHg or exercise-induced LVOT gradient > 80 mmHg c. Absence of an operational implantable cardioverter defibrillator device if there is a history of non-sustained ventricular tachycardia (> 5 beats), or an immediate family history of sudden cardiac death or arrest d. Known coronary artery disease (> 50% arterial luminal narrowing of a major epicardial vessel)
--	----------------------------------------------------------------------------------------------------------------------------------------------------------------------------------------------------------------------------------------------------------------------------------------------------------------------------------------------------------------------------------------------------------------------------------------------------------------------------------------------------------------------------------------------------------------------------------------------------------------------------------------------------------------------------------------------------------------------------------------------------------------------------------------------------------------------------------------------------------------------------------------------------------------------------------------------------------------------------------------------------------------------------------------------------------------------------------------------------------------------------------------------------------------------------------------------------------------------------------------------------------------------------------------------------------------------------------------------------------------------------------------------------------------------------------------------------------------------------------------------------------------------------------------------------------------------------------------------------------------------------------------------------------------------------------------------------------------------------------------------------------------------------------------------------------------------------------------------------------------------------------------------------------------------------------------------------------------------------------------------------------------------------------------------------------------------------------------------------------------------------------------------------------------------------------------------------------------------------------------------------------------------------------------------------------------------------------------------------------------------------------------------------------------------------------------------------------------------------------------------------------------------------------------------------------------------------------------------------------------------------------------------------------------------------------------------------------------------------------------------------------------------------------------------------------------------------------------------------------------------------------------------------------------------------------------------------------------------------------------------------------------------------------------------------------------------

	
 e. History of cardiac transplantation f. Cardiac surgery or septal reduction surgery planned in the next 6 months or having occurred within the past 6 months g. HCM believed to be caused by infiltrative disorders, glycogen storage disorders, and/or hypertensive heart disease (including genotypic or phenotypic evidence of Fabry's Disease)
Study Procedures	
Dosing will be initiated at the Baseline Visit after successful completion of the Protocol Activities during this visit. Study medication will be taken once daily in the evening (preferably 8-11p.m., with the exception of the first dose of study drug, which will be administered under the supervision of the study-site staff) on an outpatient basis for 112 consecutive days. Patients should take the study medication with a glass of water or other non-alcoholic beverage, regardless of food intake.
 
All patients will be started at an initial dose of 70 mg (2 tablets) per day. After two weeks, dose level adjustment will be made every second week according to plasma level measurements for Period 1 according to the Dose Adjustment Guidelines and Algorithm (Table 1.1).
 
At the end of Period 1 (end of Week 8), all patients will undergo CPEX examination. Following the successful completion of Period 1, patients will undergo dose adjustment every second week according to the higher target therapeutic range for plasma levels defined for Period 2 (Table 1.1).
 
At the end of Period 2 (end of Week 16), all patients will undergo CPEX testing.

Statistical Analysis	
A two-sided, one-sample t-test of the change from baseline for the end of Period 2 is planned for VO₂MAX; a power of at least 72% is expected for a sample size of 30 patients for at least a mean change from baseline of 1.2mL O₂/kg/min.

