4.4.2 Monitoring of Systemic Perhexiline and cis- and trans-Hydroxy Perhexiline

All determinations of systemic blood levels of PEX, CIS, and TRANS will be measured using the PEX-CIS assay.

On the morning of day 8 (± 1 day) (after completion of a minimum of 6 days of dosing) patients will provide a blood sample for the measurement of PEX, CIS and TRANS; the sampling timepoint will be scheduled at approximately 12h after dosing on the previous study day. The analytical results will be available within 3-5 calendar days of the blood sampling and results for PEX and CIS will be reported to the study sites. These will be used to determine the following:

- Patients deemed to be phenotypic PMs based on these results will be immediately withdrawn from study-drug dosing. A phenotypic PM is defined as a patient whose CIS:PEX ratio is <0.4 .

On the morning of day 15 (± 1 day) (after completion of a minimum of 13 days of dosing) patients will provide a blood sample for the measurement of PEX, CIS and TRANS; the sampling timepoint will be scheduled at approximately 12h after dosing on the previous study day. The analytical results will be available within 3-5 calendar days of the blood sampling and results for PEX and CIS will be reported to the study sites. These will be used to determine the following:

- The CIS:PEX ratio will be evaluated and patients with a ratio <0.4 will be further evaluated and the patient status will be discussed with the Medical Monitor.
- Dose adjustment will be decided according to the dose-adjustment algorithm presented in section 4.4.3 and Table 4.1 below.

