4.4.4 Dose-Adjustment for QTcF/JTcF Prolongation

Any dose adjustment instructions due to QTcF/JTcF prolongation will be at the direction of the ECG Core laboratory. Decisions to hold dosing until ECG Core Laboratory analysis is complete may be made at the site.

Dose adjustment for QTcF/JTcF prolongation (regardless of systemic PEX levels, unless the PEX levels and dose adjustment algorithm result in a dose reduction or discontinuation of a greater magnitude) will be done as described below for:

- a. Patients with a QRS interval \leq 100 msec WITH;
 - A prolonged QTcF $>$ 540 msec OR,
 - An increase in QTcF $>$ 75 msec over baseline AND QTcF $>$ 500 msec
- b. Whenever either the baseline or a subsequent ECG has a prolonged QRS $>$ 100 msec, changes in the JTcF will be used for all further dose-adjustment decisions throughout the remainder of the study for those patients. In a patient with a baseline or an on-study ECG showing a QRS interval $>$ 100 msec, the dose will be adjusted as described below IF;
 - The change from baseline in JTcF is $>$ 75 msec over baseline AND the JTcF interval is $>$ 410 msec OR,
 - An on-study JTcF interval is $>$ 450 msec

The dose of study drug for such patients will be stopped for 2 days and the daily dose subsequently reduced by 35 mg (for patients receiving \leq 105 mg) or 70 mg (for patients receiving \geq 140 mg) and restarted only if the QTcF/JTcF measurement has fallen back into the acceptable range for continued dosing. If the QTcF/JTcF measurement has NOT fallen back into the acceptable range after stopping drug for 2 days, the process of holding study drug and rechecking the ECG every 2 to 3 days will continue until the QTcF or JTcF limits are not exceeded and at which time study drug may be restarted at the reduced dose. The dose of study drug will not be increased any further during the remainder of the study (neither Period 1 or Period 2) if a dose reduction for QTcF or JTcF prolongation is required.

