- R. Study-drug will be dispensed once the ECG Corelab confirms that the Baseline ECG meets the entry criteria. The first study-drug dose will be administered under the supervision of the study-site staff once the study-site staff confirm that the Baseline VO₂MAX is within $\pm 20\%$ of the Screening CPEX.

Note:

- If for any reason the ECG Corelab is not able to immediately confirm the ECG outcome, the patient will return home without receiving any dispensed study-drug. In such cases, once the ECG Corelab confirmation becomes available the patient will return to the site to collect the study-drug supply. The patient will then commence study-drug dosing (defined as Day 1).
 - All Baseline ECG confirmations will be received by study sites from the ECG Corelab within a maximum of 48h.
 - Before dosing has commenced; if the centralized CPEX assessor confirms the Baseline VO₂MAX is not within $\pm 20\%$ of the Screening CPEX then the patient will not enter the study
 - Before dosing has commenced; if the centralized CPEX assessor confirms an invalid Baseline VO₂MAX the patient will be invited to repeat the Baseline CPEX test within the 28-day period allowed between Screening and the start of study-drug dosing
 - After dosing has commenced; if the centralized CPEX assessor deems the Baseline CPEX test to have been invalid or not within $\pm 20\%$ of the Screening CPEX then the patient will remain in the study and the patient's Screening CPEX result will be taken as the valid Baseline result
 - All Baseline CPEX confirmations will be received by study sites from the centralized CPEX assessor within a maximum of 48h.
- S. AEs should be documented and recorded at each visit. All AEs (serious and non-serious, and related and non-related) will be documented and recorded through the Follow-Up visit. Patients must be followed for AEs until the final required protocol visit or until all drug-related toxicities and SAEs have resolved (or are considered chronic/stable).
- T. If an AE is determined to have been the result of a PEX-CIS Assay abnormality (e.g., false positive, false negative, measurement error), it will be deemed an ADE for the purpose of device reporting.
- U. Concomitant Medications should be collected and recorded at each visit. All concomitant medications received up to and including 30 days prior to the start of study medication through the Follow-Up visit will be recorded.

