6.10 PATIENT CONTACT FOR DOSE-ADJUSTMENT INSTRUCTIONS

When the laboratory result for the levels of PEX and CIS are available the Investigators will decide if a dose adjustment is required according to the dose adjustment guidelines presented in section 4.4. Patients who require dose adjustment will be contacted immediately by study-site personnel who will ensure that the dose-adjustment required is fully understood by the patient who will initiate the required dose adjustment at their next scheduled study drug dosing.

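### Read literally, the exception to the QT rule drops the ECG-cleared restart whenever the plasma-level table gives the larger dose cut or stop

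*Protocol*

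**What the plan says.** The QT rule is in the protocol synopsis (Dose Adjustment Guidelines and Algorithm, item 6) and in Section 4.4.4. It has four parts:

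- a stop: "The dose of study drug for such patients will be stopped for 2 days";
- a cut of 35 mg for patients on 105 mg or less, or 70 mg for those on 140 mg or more;
- a condition on restart: study drug is "restarted only if the QTcF/JTcF measurement has fallen back into the acceptable range for continued dosing", with the hold and ECG rechecks every 2 to 3 days continuing until then;
- no later dose increase once a reduction for QTcF/JTcF prolongation has been required.

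The rule applies whatever the PEX level, "unless the PEX levels and dose adjustment algorithm result in a dose reduction or discontinuation of a greater magnitude". Tables 1.1 and 4.1 set the PEX-level changes as fixed stops of 0, 1, 3 or 7 days and cuts of 1 to 5 tablets, down to a 35 mg floor. They contain no ECG condition.

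On responsibility, Section 4.4.4 says "Any dose adjustment instructions due to QTcF/JTcF prolongation will be at the direction of the ECG Core laboratory" and "Decisions to hold dosing until ECG Core Laboratory analysis is complete may be made at the site". For PEX-level changes, Section 6.10 says "the Investigators will decide if a dose adjustment is required according to the dose adjustment guidelines presented in section 4.4". On timing, Section 4.4.2 has PEX results available "within 3-5 calendar days of the blood sampling and results for PEX and CIS will be reported to the study sites". Section 2.8.3 restates the QT triggers but not the exception. SAP Section 3.5.2 describes titration without mentioning the QT rule.

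**The concern.** The exception is attached to the QT adjustment as a whole, and that adjustment includes the restart condition. If the PEX table takes over, the text leaves nothing that ties the restart to the ECG. The ban on later increases is also in doubt. It depends on a reduction having been required for QTcF/JTcF prolongation, and here the table supplied the reduction. In Period 2, Table 4.1 would then add one tablet at 101-300 ng/mL and two at 100 ng/mL or below.

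This runs against the purpose stated in Section 2.8.3, which is to minimize QT risk. Section 2.5 reports mean QTcF effects of 15.3 msec at a mean Cmax of 278.6 ng/mL and 22.8 msec at 677.9 ng/mL. On the literal reading, a patient with the higher level loses the ECG check, while a patient with the same ECG and a lower level keeps it. Two sites could follow the same text and act differently.

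**Working it through.** **Inputs.** The QT rule comes from Section 4.4.4 and the PEX rule from Table 4.1. Allowed doses are 35-210 mg in Period 1 (6 levels) and 35-280 mg in Period 2 (8 levels), in 35 mg steps. The plan gives no figure of its own to reproduce.

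**Combinations with a table reduction.** Period 1: 6 doses × 7 bands (above 300 ng/mL) = 42. Period 2: 8 doses × 5 bands (above 500 ng/mL) = 40. Total 82, of which 7 + 5 = 12 are at 35 mg, leaving 70 at 70 mg and above.

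**Formulas.** Real table cut = dose − max(35 mg, dose − tablets × 35 mg). QT cut = 35 mg if dose ≤ 105 mg, 70 mg if dose ≥ 140 mg. QT stop = 2 days.

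**Comparison at 70 mg and above.**

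| | Period 1 | Period 2 | Total |
|---|---|---|---|
| Table cut larger, table stop 0 days | 5 | 0 | 5 |
| Table cut larger, table stop 1 day | 4 | 7 | 11 |
| Table cut larger, table stop 3 days | 4 | 6 | 10 |
| Table cut larger, table stop 7 days | 8 | 6 | 14 |
| **Table cut larger, all** | **21** | **19** | **40** |
| Cuts equal | 11 | 11 | 22 |
| Table cut smaller | 3 | 5 | 8 |

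In 10 + 14 = 24 combinations the table is stricter on both cut and stop, so the exception applies on any reading of greater magnitude. In 5 + 11 = 16 the table has the larger cut but the shorter stop. In 5 of the 22 equal-cut combinations (all at 70 mg) the table's stop is longer. If either component is enough, the table takes over in 40 + 5 = 45. The QT rule stands on every reading in 70 − 45 = 25. None of the 24, 40 or 45 has a stated ECG-cleared restart.

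**Example that does not turn on the meaning of greater.** Period 1, 140 mg, QTcF above 540 msec, PEX 701-900 ng/mL. Table: 3-day stop; 140 − 4 × 35 = 0, raised to the 35 mg floor, a cut of 105 mg. QT rule: 2-day stop, cut of 70 mg, restart only when the ECG clears. The table is stricter on both counts. On the literal reading the patient restarts at 35 mg after 3 days whatever the ECG shows; on the protective reading the hold continues.

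**Timing.** Core-laboratory turnaround is given for Baseline only: "All Baseline ECG confirmations will be received by study sites from the ECG Corelab within a maximum of 48h". I assume the same 0-2 days on study. If the hold starts when the ECG is read and the recheck follows 2 days later, the first recheck falls on Day 2, 3 or 4. The PEX result arrives on Day 3, 4 or 5. Of the 3 × 3 = 9 pairings, the PEX result comes before the recheck in 1, on the same day in 2, and after it in 6. In those 6 the clause matters only if the recheck is still out of range. A 3-day turnaround would put the first recheck on Day 5, so the PEX result would then never come after it.

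**The case against.** The strongest reply is that the clause concerns only the size of the adjustment: it stops the QT rule from softening a stricter PEX action. Section 4.4.4 refers to such patients, meaning all those beyond the limits, when it sets the ECG condition. That supports keeping the check for everyone, and it may well be what was intended. It is still an inference, and the text does not state it.

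The practical points are fair and narrow the exposure:

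- The QT rule runs by default until the PEX result arrives, so the 2-day stop has usually been served. The 16 shorter-stop combinations are mostly moot.
- Synopsis item 3 and Section 4.4.3 generally allow one dose adjustment per two weeks, with Medical Monitor contact if the investigator wants another. A table change on top of a QT reduction arguably needs that contact.
- The core laboratory directs QT changes, and the site may hold dosing until the ECG is read.
- Of the 40 combinations, 10 are above 1,200 ng/mL, where Section 4.5 calls for continuous cardiac monitoring.
- A trigger is likely to be uncommon. One route needs a rise above 75 msec, against a mean effect of 22.8 msec at 677.9 ng/mL, and only about 33 patients are planned.

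None of these makes ECG clearance a condition of restart once the table governs.

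A reader might also infer that nobody holds both the PEX level and the ECG. The documents do not support that: PEX results go to the sites, SAP Section 3.2.5 has ECG traces made available to the site investigator, and Section 6.10 sends the investigator to all of Section 4.4. That reference includes the same exception, so it does not settle its meaning.

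**Conclusion.** The gap is real and limited. On its plain words the exception lets the PEX table replace the QT procedure, including the ECG-cleared restart and arguably the ban on later increases. At 70 mg and above the table's cut is larger in 40 of 70 combinations, and in 24 of those it is stricter on both counts. These figures rest on Table 4.1 with the 35 mg floor applied. They say nothing about how many patients would be affected, which the documents do not allow one to estimate.

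The main exposure is a patient whose ECG is still out of range, or not yet read, when the PEX result arrives on Day 3-5. How often the two events overlap depends on an on-study turnaround that the protocol does not give.

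A reader might conclude that the protocol directs sites to re-dose patients with a prolonged interval, or that 40 of 70 measures risk. Neither follows: a protective reading is available, and the combinations are unweighted. The primary analysis is not affected.

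**What to change.** Replace the exception in synopsis item 6 and in Section 4.4.4 with:

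> For any patient meeting a QTcF/JTcF criterion, the larger of the two dose cuts and the longer of the two stops apply; in every case study drug is restarted only after the QTcF/JTcF is back within limits, and the dose is not increased again during the study, whatever the PEX level.

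The cost is one amendment to two places. Compared with the table's own stop, the minimum hold is 1 day longer in 11 combinations and 2 days longer in 5 (16 in all), much of it already served by the time the PEX result arrives. A few extra ECG rechecks follow, of the kind the QT rule already uses. No patients are added.

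This sentence does not settle the patient already on 35 mg, for whom the QT cut leaves 0 mg while the lowest listed dose is 35 mg. That case is better left to the sponsor and Medical Monitor: a fixed stop there could become a new discontinuation rule and lose completers from the roughly 30 expected.
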